maintenance after PCa surgery on obesity-driven PCa biomarkers. Forty men with stage T1 or T2 PCa scheduled to undergo RP will be randomized to receive a weight management program (intervention; n = 20) or standardized education materials (control; n = 20). Our pilot work has established that men awaiting RP are very motivated and embrace the pre-surgical intervention as a means to cope with anxiety by improving their health. We employ a weight loss intervention that emphasizes competition, autonomy, technology, cost savings, and male-specific barriers to change—factors that prior studies have found to be important to successful weight loss interventions among men. We also examine critical QoL factors that could affect the feasibility of the intervention in future trials and clinical practice. Our hypotheses and specific aims are:

1. *To test the impact of weight management on obesity-driven PCa biomarkers taken at baseline, 1 week prior to surgery, surgery and 6 months after surgery.

Hypothesis 1.1: Immune suppressive factors will respond to the intervention with reduced total MDSC (Lin- CD11b+ CD33+) and monocytic MDSC (Lin- CD11b+ CD33+ CD14+ CD15-) counts compared to baseline values and to the control group. **Primary Objective**

Hypothesis 1.2: Participants in the intervention group will have a more favorable chemokine, adipokine, and cytokine profile than the participants in the control group.

2. To evaluate how weight management affects weight loss, body composition, and weight maintenance in overweight and obese men with localized PCa.

Hypothesis 2.1: The intervention will lead to significant weight reduction compared to the control group from baseline to 1 week prior to surgery.

Hypothesis 2.2: The intervention will reduce body fat and maintain lean body mass as measured by Dual Energy X-Ray Absorptiometry (iDXA) scans from baseline to 1 week prior to surgery.

Hypothesis 2.3: The intervention will lead to weight maintenance (<3% regain) 6 months after RP.

3. To test the impact of weight management on QoL in PCa survivors.

Hypothesis 3.1: The intervention will report better urinary function and lower urinary bother compared to control 6 months after RP as measured by the Expanded PCa Index Composite (EPIC) Instrument-26.

Hypothesis 3.2: The intervention will improve sexual function and QoL 6 months after RP as measured by the EPIC-26.

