All participants will receive a book, "[name] to Surviving Prostate Cancer" by Patrick C. Walsh and Janet Farrar Worthington and a booklet from the American Institute for Cancer Research, "Heal Well, A Cancer Nutrition Guide". Participants randomized to the intervention will undergo the weight loss program for 4-16 weeks prior to surgery and a weight maintenance program for 26 weeks after surgery, while patients randomized to the control group will only receive the book and booklet at baseline. The same assessments will be measured and analyzed in all participants at the clinic visits at baseline, 1 week prior to surgery, and 6 months post-operation. Major deviations from the protocol will be recorded. However all evaluable patients will be analyzed according to intention to treat.

Participants. Overweight or obese men scheduled for RP with newly diagnosed PCa will be recruited from the University of Kansas (KU) Hospital Urologic Clinic and the KU Cancer Center (See **Table 1**). The Department of Urology at the KU Medical Center is the only academic urology program in the region performing 477 prostatectomies over the past 2 years. Co-investigator, J. [name], is the co-director of operative services. Our recruitment goal is 1 participant per month. [name] or his team of urologic surgeons will describe the study to candidates for RP and provide the name and medical record number of interested patients to [name] study team. Patients with newly diagnosed PCa will be offered entry into the trial during the discussion of radical RP which typically has a waiting period anywhere from 4-16 weeks from consult to scheduled surgery. Our pilot data in the RP population show 80% are White; 20% are Black/African American (AA); and 10% are Hispanic men.

Table 1: Inclusion/Exclusion Criteria

Inclusion Criteria	Inclusion Justification
Men newly diagnosed with PCa who are scheduled for RP (T1 or T2)	Assure intervention is aimed at a targeted population to reduce heterogeneity
Minimum age of 50	Lower age limit to minimize aggressive cancer phenotypes
BMI 25-45 kg/m2	If men drop to a BMI of 22, they will be routed into the maintenance phase of the intervention.; upper limit for feasibility for iDXA measurements
Internet access*	Assure access to daily diet/physical activity tracking viewed by participant and weight loss coach
Exclusion Criteria	Exclusion Justification
History of 5 alpha reductase inhibitors prior 3 months	Avoid confounding effects of treatment

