Immune Biomarkers		X	X	X
Inflammation Biomarkers		X	X	X
Cardiometabolic Markers		X	X	X
Microbiome		X	X	X

Justification of sample size: We powered this study for aims 1 and 2, but aim 3 and 4 are exploratory. The power calculations used effect sizes and standard deviations from our pilot study (ClinicalTrials.gov: NCT02252484). The primary objective is to reduce obesity-driven biomarkers (MDSCs) of PCa recurrence and death. Our pilot study showed that weight loss of 1.2 pounds/week corresponds to a decrease in MDSC by 1.4 counts/week. Group sample sizes of 17 and 17 achieve over 80% power to detect a change in MDSC of 1.2 per week between the intervention and control groups with standard deviations of 1.6 and 0.3 (obtained from our pilot study) with a significance level of 0.05 using a two-sided, two-sample t-test. Secondary objective: Thirty-four participants will detect weight change as low as 0.5 kg/week between the intervention and control groups using the standard deviations of 0.6 and 0.1, from our pilot study. Weight maintenance will also be examined. If the intervention maintains their weight loss within 3%, 17 patients will give power over 80% to detect equivalency in the intervention group assuming the moderate correlation of 0.4 using paired t-tests. Tertiary objectives to assess the impact of weight loss on QoL using the EPIC-26 tool are exploratory. The results will be used to calculate effect sizes for a definitive, large multi-site clinical trial.

Statistical Analysis Prior to initiating outcome analyses, we will summarize the baseline characteristics of the data. Tests will be considered significant if the *P*-value is less than 0.045 for the final analysis. Our data may include missing observations related to either attrition or nonresponse and this type of missing data can reasonably be assumed to be random. We will run an intention to treat analysis for all outcomes. Comparisons will be carried out separately for the weight loss phase (enrollment to 1 week prior to surgery) and the weight maintenance phase (1 week prior to surgery to 6 months after surgery). Since patients will be on the pre-surgical phase for varying durations of time, we will assess the rate of weight loss between the two groups. A two-sample t-test will be used to assess the differences in outcomes between the two groups. The significance of within-group differences will be assessed using a paired t-test.

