Therefore, 34 eligible, randomized patients will provide sufficient power for both aims 1 and 2. However, based on our pilot study, we anticipate that 10% of patients will drop out by the 6 months follow up. Incorporation of this dropout rate inflates the required sample size by a

factor of $34/0.9 = 38$ eligible patients. Finally, assuming a 5% ineligibility rate, a total of $n = 40$ registered patients will be required. A single interim analysis for efficacy will be conducted when 50% of patients achieve their endpoint, at the alpha = 0.005 level. Accordingly, the final analysis will be conducted at the alpha = 0.045 level.

Potential difficulties

- *Tracking/technology.* In our pilot study, many participants were unfamiliar with the technology used and they had never tracked diet or physical activity before. For these participants, we initially offered paper journals so they could track their meal plans by hand. Then, coaches would help them enter the data at the visits. We will offer the same strategy in this project. Also, some participants wanted to remove their accelerometers after surgery because their step counts dropped so low. Our team affirmed that disruptions in sedentary activity (as prompted by the Vivofit® 3) is more important for their health than absolute step counts in the early days after surgery. Coaching participants to reframe negative feelings has helped to overcome this obstacle.

PROTECTION OF HUMAN SUBJECTS

Recruitment Potential subjects will be approached by their urologist or oncologist and informed about the possibility of research participation. Patients who are interested in learning more about participation will be introduced to the study coordinator who will then explain the study in detail. The potential subjects will have the opportunity to read the consent form in the absence of the PI and study team. It will be explained to the subjects that the study is voluntary and that they may discontinue at any time without prejudice.

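### Intention to treat is promised for all outcomes but limited elsewhere to an undefined evaluable set, the named t-tests drop men without follow-up, and the plan does not settle whether its 40 men are registered or randomised.

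*Combined protocol and SAP*

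**What the plan says.** The analysis population is described twice. In Research Design and Methods, Aim 1, just after saying that major deviations will be recorded, the plan states: "However all evaluable patients will be analyzed according to intention to treat". The Statistical Analysis section states: "We will run an intention to treat analysis for all outcomes". Evaluable is not defined anywhere, and nothing says who would judge it or when.

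On missing values, Statistical Analysis says that "this type of missing data can reasonably be assumed to be random". The only methods it names are a two-sample t-test between arms and a paired t-test within arms. The one imputation rule in the document, under Aim 3, concerns single unanswered EPIC-26 items.

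The counts are also given twice. Aims and Hypothesis says "Forty men with stage T1 or T2 PCa scheduled to undergo RP will be randomized to receive a weight management program" or control materials, 20 per arm, and the Aim 1 design text repeats 20 and 20. The sample-size text that follows Statistical Analysis starts from "Therefore, 34 eligible, randomized patients will provide sufficient power for both aims 1 and 2". It then says "we anticipate that 10% of patients will drop out by the 6 months follow up", inflates to "factor of $34/0.9 = 38$ eligible patients", and, "assuming a 5% ineligibility rate", arrives at 40 registered patients. Table 3 places registration in the screening column, before baseline, and does not show when randomisation happens.

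**The concern.** The two population statements are different rules. An unqualified intention-to-treat analysis keeps every randomised man in his assigned arm. One limited to evaluable men lets some be set aside after allocation, on a criterion nobody has written down. The Statistical Analysis wording does not close the gap, because a t-test on change uses only men who have both values.

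This matters because losses here may not be random. The Control group paragraph withholds coaching, technology and meal replacements from controls, so participants and coaches necessarily know the arm. The plan itself remarks that motivation wanes after surgery. If intervention men who respond poorly are the ones without follow-up, the remaining contrast favours the programme and would still be reported as intention to treat. With 20 men per arm, a few such losses are visible in the result.

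The registered-versus-randomised discrepancy adds a second uncertainty: a reader cannot tell how many men the randomised comparison is meant to contain.

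**Working it through.** **1. Reproduce the plan's power.** Inputs from Justification of sample size: 17 per arm, difference 1.2 MDSC counts/week, SDs 1.6 and 0.3, two-sided 0.05.
- Standard error = √(1.6²/17 + 0.3²/17) = √(2.65/17) = 0.395.
- Noncentrality = 1.2/0.395 = 3.04; Welch degrees of freedom = 17.1.
- Power = 81.7%, which agrees with the stated figure of over 80%. At the final-analysis level of 0.045 it is 80.3%.

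**2. Reproduce the sample-size chain.**
- Dropout: 34/0.9 = 37.8, rounded up to 38.
- Ineligibility: 38/0.95 = 40.0.
- Both steps are arithmetically correct. The question is what the 40 denotes.

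**3. Planned loss after allocation under each reading.**

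| Reading | Randomised | Ineligible after allocation | Dropout by 6 months | Loss |
|---|---|---|---|---|
| Ineligible men leave before allocation | 38 | 0 | 4 | 4/38 = 10.5% |
| All 40 are randomised | 40 | 2 | 4 | 6/40 = 15.0% |

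Without rounding, the second figure is 1 − 0.95 × 0.90 = 14.5%. Dropout accounts for all of the first loss and for 4 of the 6 men in the second.

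**4. Which reading do the documents support?** The sample-size text says registered, and Table 3 pairs registration with screening; both point to the first. The aims and design text randomise forty, and the sample-size text attaches eligible as a separate qualifier to its 34 randomised men; both point to the second. The documents do not settle it.

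**5. Illustration of the possible size.** Assume k of 20 intervention men are lost before the pre-surgery visit, that their change equals the control mean (no response), and that the men who remain show the planned difference. The difference over all randomised men is then 1.2 × (20 − k)/20, and the analysed figure overstates it by a factor of 20/(20 − k).

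| k | All-randomised MDSC difference per week | Overstatement |
|---|---|---|
| 1 | 1.14 | 20/19 = 1.05 |
| 2 | 1.08 | 20/18 = 1.11 |
| 3 | 1.02 | 20/17 = 1.18 |

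For weight at k = 3, 0.5 × 17/20 = 0.425 kg/week, the same 18%.

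**The case against.** **The sentence containing evaluable seems meant to be inclusive.** It follows the remark on protocol deviations and opens with a contrast, so the likely intent is to keep deviators in. A man who abandons the diet but attends his visit has data, and nothing removes him. This stands as a reading of intent, and it makes missing outcome data the likeliest meaning of evaluable. It does not supply a definition, and it does not stop the t-tests from dropping men without a follow-up value.

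**Removal of randomised men as ineligible is not written down.** A reader might infer that two of the 40 randomised men will be set aside with their arm known. No section says so; that reading comes from joining two inconsistent counts. The objection stands, and the point is limited to the inconsistency.

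**The 15% is neither a ceiling nor a count of exclusions.** Four of the six men are expected dropouts. An undefined term caps nothing, so calling it an upper limit would also be wrong. The 10% dropout runs to 6 months after surgery, whereas the per-week rates concern the pre-surgical phase, where loss may be lower. This stands, and it is why the 18% is only an illustration.

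**Unequal loss need not cost power.** At 0.045, intervention/control splits of 16/18 and 15/19 give 77.6% and 74.6%, but 18/16 and 19/15 give 82.7% and 84.8%, against 80.3% at 17/17. No directional power claim is justified.

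**A mixed model also assumes data missing at random.** True, and men with only a baseline value add almost nothing to it. That is the reason for adding a sensitivity analysis.

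**The plan does not call itself open-label.** Masking of laboratory staff and assessors is not described, and the Medical Monitor text mentions unblinding. Only participants and coaches can be said to know the arm.

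**Conclusion.** The concern holds in a limited form. The plan states two different analysis populations, one resting on an undefined term, and names methods that do not deliver the intention-to-treat analysis it promises for biomarkers and weight. It also counts 40 as registered in one place and randomised in others. Planned loss after allocation is 10.5% or 15% depending on which is meant, and is mostly dropout by 6 months.

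The documents do not support a stronger conclusion that randomised men will be discarded as ineligible, or that the result will be biased by a known amount. The 18% overstatement depends on three assumptions: 3 of 20 intervention men lost, lost before the pre-surgery visit, and no response in any of them. With one or two such men it is 5% or 11%; if lost men respond like the others it is nil.

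The plan should be amended before analysis. The concern is about the definition and handling of the analysis set, not about the sample size.

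**What to change.** 1. In the Aim 1 text, delete evaluable. Define the analysis set as all randomised men in their assigned arm, regardless of adherence or ineligibility found later.
2. Reconcile the sample-size text with the aims and design text: state either that eligibility is confirmed before randomisation, or that randomised men later found ineligible stay in the analysis.
3. Describe the 34 as the number expected to have data, not as the analysis population.
4. Replace the t-tests on change with a mixed model using all available visits, with actual time on the pre-surgical phase included so that the per-week rate is kept. Say how a man without a surgery-anchored visit enters the model.
5. Add one sensitivity analysis in which intervention men without follow-up are given the control-arm mean change.

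The cost is wording and a little more analysis, with no additional patients. The estimated effect may be smaller. In the three-man illustration, a difference of 1.02 with 20 per arm, unchanged SDs and 0.045 has about 74% power, compared with 87.0% for 1.2 with all 40 observed. The sensitivity analysis should therefore be read as a check on robustness, not as a second primary test.

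### Weight maintenance is an upper limit on regain in Hypothesis 2.3 but equivalence within 3% in the power statement, and the planned paired t-test tests neither

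*Combined protocol and SAP*

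**What the plan says.** Three places bear on the maintenance endpoint.

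- Aims and Hypothesis, Hypothesis 2.3: "The intervention will lead to weight maintenance (<3% regain) 6 months after RP". This caps weight gain. It sets no limit on further loss.
- Justification of sample size: the sentence opens with the condition "If the intervention maintains their weight loss within 3" percent and then claims that "17 patients will give power over 80% to detect equivalency in the intervention group", "assuming the moderate correlation of 0.4 using paired t-tests". It gives no lower limit, no SD of weight change, no alpha and no statement of which weight the 3% refers to.
- Statistical Analysis: "The significance of within-group differences will be assessed using a paired t-test". No equivalence or non-inferiority procedure and no 3% margin appear there. The maintenance phase is defined as running from 1 week before surgery to 6 months after it.

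Two neighbouring figures do not fill the gaps. The weight SDs, "using the standard deviations of 0.6 and 0.1, from our pilot study", belong to the between-group comparison of weekly weight change. The 0.05 level, "with a significance level of 0.05 using a two-sided, two-sample t-test", belongs to the MDSC calculation, and the final analysis uses 0.045.

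**The concern.** A cap on regain is a one-sided (non-inferiority) criterion. Equivalence within a margin, as the word is ordinarily used, has a lower limit as well. The two can give different answers for the same data when the arm goes on losing weight: regain is below 3%, yet the lower confidence limit may lie beyond a 3% loss. The planned paired t-test asks a third question, whether mean change differs from zero. A non-significant result there does not show maintenance under either definition, and a significant one can arise when either definition is met.

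What is at stake is the conclusion on one secondary hypothesis. With the criterion open, it could be settled after the data are seen. The sample-size section also says that the study is powered for aims 1 and 2, so the maintenance power is a formal claim that should refer to the hypothesis as written.

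**Working it through.** **Inputs from the documents.** n = 17 in the intervention arm; margin 3%; within-patient correlation 0.4; stated power over 80%.

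**Assumed, because not given.** The 3% is a percentage of body weight at 1 week before surgery; alpha is 5% per side; the SD of percent change (SD_diff) is 3% to 5%.

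**1. The plan's own figure.** It cannot be reproduced without an SD. Instead one can solve for the largest SD_diff that gives 80% power with n = 17 and a true change of zero. A per-visit SD converts by SD_diff = SD × √(2 × (1 − 0.4)) = 1.095 × SD.

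| Test | Largest SD_diff, alpha 0.05 | Per-visit SD | Largest SD_diff, alpha 0.045 |
|---|---|---|---|
| One-sided, regain below 3% | 4.76% | 4.35% | 4.65% |
| Equivalence, within ±3% | 4.04% | 3.69% | 3.96% |

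The claim is therefore attainable under either rule if the SD is small enough. It can be neither confirmed nor refuted.

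**2. Where the two rules part on observed data.** The one-sided rule needs mean + t × SE < 3. Equivalence also needs mean − t × SE > −3. With t(0.95, 16 df) = 1.746 and SE = SD_diff/√17:

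- SD_diff 3%: half-width 1.746 × 3/4.123 = 1.27, so equivalence fails at an observed loss beyond 3 − 1.27 = 1.73%.
- SD_diff 4%: half-width 1.69, threshold 1.31%.
- SD_diff 5%: half-width 2.12, threshold 0.88%.

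Example: an observed loss of 1.5% with SD 4% gives an interval of −3.19% to +0.19%. The upper limit is well below +3%, so Hypothesis 2.3 is met. The lower limit is below −3%, so equivalence is not shown.

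**3. Probability of success by true mean change** (exact t-based power, n = 17, 5% per side; one-sided / equivalence):

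| True mean change | SD_diff 3% | SD_diff 4% | SD_diff 5% |
|---|---|---|---|
| +2% | 37% / 37% | 26% / 26% | 20% / 19% |
| +1% | 84% / 84% | 63% / 62% | 47% / 41% |
| 0 | 99% / 98% | 91% / 81% | 77% / 53% |
| −1% | 100% / 84% | 99% / 62% | 93% / 41% |
| −2% | 100% / 37% | 100% / 26% | 99% / 19% |
| −3% | 100% / 5% | 100% / 5% | 100% / 5% |

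On the regain side the rules nearly agree, with a gap of at most about 6 points. On the loss side they diverge, decisively at a mean loss near 3%.

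**4. The planned paired t-test of difference** (two-sided 5%, n = 17, SD_diff 3%, 4%, 5%). At a true regain of 2%, which meets Hypothesis 2.3, it is significant in 73%, 49% and 34% of trials. At a true regain of 3%, which does not meet it, it is significant in 97%, 83% and 64%, and so non-significant in 3%, 17% and 36%. Neither outcome of this test corresponds to either maintenance criterion.

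**The case against.** The strongest reply is that the two-sided rule is an inference. No −3% limit and no two one-sided tests procedure are written, and the sample-size sentence speaks of keeping the weight loss, which may be a loose restatement of the cap on regain. That stands: the documents do not state two explicitly conflicting limits. But if the one-sided meaning was intended, equivalency is the wrong term and the sentence still needs correcting.

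Three stronger readings are tempting and are not supported.

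- A reader might infer that any arm that goes on losing weight fails equivalence. It does not. A true mean loss below 3% lies inside both definitions, and at a 1% loss equivalence is still shown in 84% to 41% of trials. What splits the rules is a lower confidence limit beyond −3%.
- A reader might infer that further loss is the expected result, since the post-surgical curriculum in Table 2 asks for daily exercise. The documents point at least as much to stability or regain: AIM 2 says that motivation falls off after surgery, Preliminary Studies reports weight maintained at twelve weeks, and Potential difficulties describes low step counts after surgery. In that region the rules nearly agree.
- A reader might infer that the power statement is wrong or the trial too small. Every result that passes equivalence also passes the one-sided rule. If 17 patients give over 80% power for equivalence, they give at least that for Hypothesis 2.3 under the same assumptions.

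It is also fair to say that stability within two limits is a legitimate meaning of maintenance. The choice is the sponsor's, but it has to be written once and tested. And since no equivalence test is planned, a failed equivalence verdict would not be issued under the current analysis text. That makes the analysis section part of the problem, so editing the sample-size sentence alone would not be enough.

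**Conclusion.** The point holds as an inconsistency on a secondary endpoint. The hypothesis, the power statement and the analysis text describe three different questions, and nothing in the documents reconciles them. The size of the inconsistency depends on the unstated SD. For an assumed SD of change of 3% to 5% at 5% per side, a two-sided test would begin to contradict Hypothesis 2.3 at an observed mean loss of about 1.7% to 0.9%. At zero true change the two rules differ by 1 to 23 points of power (99% against 98% at SD 3%; 77% against 53% at SD 5%, from unrounded 76.5% and 53.1%).

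The stated power is unverifiable rather than wrong. The primary MDSC endpoint, the 34 evaluable patients and the total of 40 are not affected. The correction is worth making because it is cheap and removes a choice that could otherwise be made after seeing the data.

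**What to change.** Use one criterion in both the sample-size and the Statistical Analysis text.

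1. State that maintenance is shown if the one-sided upper confidence limit for mean percent weight change in the intervention arm, from 1 week before surgery to 6 months after surgery, is below +3%. This matches Hypothesis 2.3 and fixes the reference weight.
2. In Justification of sample size, replace the equivalency wording with this criterion and restate the power for 17 patients, giving the SD of percent change and the alpha assumed.
3. In Statistical Analysis, name this test for Hypothesis 2.3 in place of the paired t-test of difference.

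If the sponsor does intend two-sided stability, it should instead write both limits into Hypothesis 2.3, specify the equivalence test in the analysis, and give the power for that test.

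The cost is a few sentences and one recalculated power figure. No further patients, visits or data are needed, and at the same n and alpha the one-sided test has at least as much power as equivalence.

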Official Title: **Weight management Aimed to Reduce Risk and Improve Outcomes from Radical Prostatectomy (WARRIOR)**

NCT Number: NCT03261271

Approval Date: March 23, 2020

**Weight management Aimed to Reduce Risk and Improve Outcomes from Radical
Prostatectomy
WARRIOR**

Principal Investigator: [name], RD, CSO
Department of Dietetics & Nutrition
Associate Professor
University of Kansas Medical Center
School of Health Professions
Department of Urology
[name] [name]
[contact] [contact]
e-mail: [contact]

Co-Investigators: [name], FACS
[name], RD

Study Coordinator: [name], RD
[name], Department of Urology

Statistician: [name]

Institutions: University of Kansas Cancer Center
[name]
[name]
[contact] [contact]

University of Kansas Medical Center
[name]
[name]

Funding:
[name] is supported by a Research Scholar Grant, RSG-17-050-01 - NEC, from the American Cancer Society. Project title: Weight Loss for Obesity-Driven Biomarkers of Prostate Cancer Progression

Protocol Version Date: March 23, 2020

Document Type: Amendment Protocol Version 3.0

Version Number: v4.0

CTRC Protocol #: 284

HSC #: STUDY00141060

PRMC approval date: 06/09/2017

Study name: **Weight management Aimed to Reduce Risk and Improve Outcomes from Radical Prostatectomy**

Nickname: **WARRIOR**

[figure not shown]
Protocol Synopsis

Title	Weight management Aimed to Reduce Risk and Improve Outcomes from Radical Prostatectomy WARRIOR
Nickname	
Primary Objective	To test the impact of weight management on obesity-driven prostate cancer biomarkers of recurrence and mortality taken at baseline, 1 week prior to surgery, and 6 months after surgery.
Secondary Objective	To evaluate how weight management affects weight loss, body composition, and weight maintenance in overweight and obese men with localized prostate cancer.
Sample Size	40
Summary of Subject	Men undergoing a prostatectomy
Eligibility Criteria	
▪ Minimum age of 50▪ BMI 25-45 kg/m²▪ Minimum 4 weeks lag-time until prostatectomy▪ Internet access▪ iDevice* (iPad, iPod, iPad mini, iPhone) *iDevices may be issued by the research team to be returned at the end of the study.
Procedures	Participants will undergo a pre-surgical weight loss intervention prior to scheduled prostatectomy and a 6-month post-surgical weight maintenance program after prostatectomy.

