Sample collection, processing, and analysis. Whole blood and fecal samples will be collected at baseline, 1 week prior to surgery, and 6 months post-operation. Fresh prostate tissue will be collected and flash-frozen from the RP and stored in vapor phase nitrogen. Paraffin-embedded prostate tissue will also be collected from the RP. Since the majority of PCas originate in the peripheral zone, we will obtain samples from 4 quadrants of the prostate peripheral zone in normal/tumor pairs. H&E staining will determine malignant versus benign tissue. Periprostatic adipose tissue will be collected from the RP.

Blood Immune biomarkers. The primary objective of this project is to assess the impact of weight loss before and weight maintenance after PCa surgery on immunosuppressive factors compared to a randomized control. Although our pilot data suggest MDSCs are a logical target for obesity-driven PCa progression, our team is aware of how other immune cells play an interconnected role. We carefully chose biomarkers that fit our hypothesis within the budget constraints, we will analyze MDSCs and their subtypes, Natural Killer (NK) Cells, and regulatory T cells (Tregs). MDSC subpopulations are defined according to published methods⁷³ of grouping granulocytic (Lin⁻ CD11b⁺ CD33⁺ CD14⁻ CD15⁺), monocytic (Lin⁻ CD11b⁺ CD33⁺ CD14⁺ CD15⁻), and immature (Lin⁻ CD11b⁺ CD33⁺ CD14⁻ CD15⁻). Natural Killer (NK) cells are defined by CD56 and CD16 expression, and regulatory T cells (Tregs) by CD4+, CD25+, FoxP3+ expression in the blood. Please see our recent publication⁹ for additional information about our method.

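### The primary MDSC hypothesis names no visit or phase, so the plan does not say which test the 0.005/0.045 alpha split covers or what triggers the interim look

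*Combined protocol and SAP*

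**What the plan says.** The Protocol Synopsis gives the primary objective as the effect on biomarkers "taken at baseline, 1 week prior to surgery, and 6 months after surgery", without choosing among these visits. In Aims and Hypothesis, Hypothesis 1.1 carries the Primary Objective label: "Immune suppressive factors will respond to the intervention with reduced total MDSC" and monocytic MDSC "counts compared to baseline values and to the control group". It gives no time point. Hypothesis 2.1, by contrast, fixes its window: "significant weight reduction compared to the control group from baseline to 1 week prior to surgery". Hypotheses 2.2, 2.3, 3.1 and 3.2 also name a window or visit.

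Under Main Outcomes (Blood Immune biomarkers), the primary objective is to "assess the impact of weight loss before and weight maintenance after PCa surgery on immunosuppressive factors compared to a randomized control", which covers both phases.

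The Statistical Analysis section says "We will run an intention to treat analysis for all outcomes" and "Comparisons will be carried out separately for the weight loss phase (enrollment to 1 week prior to surgery) and the weight maintenance phase", with significance at P < 0.045. It sets no hierarchy between the phases, no multiplicity adjustment and no rule that both must succeed. The text after it adds: "A single interim analysis for efficacy will be conducted when 50% of patients achieve their endpoint, at the alpha = 0.005 level". The final analysis is then at 0.045. The endpoint in that sentence is not defined.

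**The concern.** The 0.005 + 0.045 allocation pays for two looks at one comparison. With two phase comparisons on the same marker and no statement of which one decides, a chance difference in either phase could be presented as meeting the primary objective.

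The phases also ask different questions. The maintenance comparison starts from the pre-surgery value, so it does not measure reduction from baseline. The plan gives no maintenance-phase MDSC effect or standard deviation to support the sample size.

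The interim look has the same gap. Its timing depends on whether the endpoint is the pre-surgery or the 6-month value. Under Safety Monitoring, the medical monitor may recommend ending accrual early on the basis of interim outcome analyses, so a real decision depends on the answer.

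**Working it through.** **Inputs from the plan.** 17 per arm; MDSC difference 1.2 per week; SDs 1.6 and 0.3; two-sided 0.05 in the power calculation; 0.005 interim at 50% and 0.045 final; 10% dropout; 5% ineligible; 40 registered; recruitment goal 1 man per month; pre-surgical phase 4-16 weeks; post-surgical phase 26 weeks.

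**1. The plan's own figures reproduce.**
- Standard error = sqrt(1.6²/17 + 0.3²/17) = sqrt(2.65/17) = 0.395. Standardised effect = 1.2/0.395 = 3.04.
- Power at 0.05: 0.860 (normal), 0.838 (pooled t, 32 df), 0.817 (Welch, 17.1 df). All exceed 80%.
- 34/0.9 = 37.8, so 38; 38/0.95 = 40.
- 0.005 + 0.045 = 0.05.

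**2. One test, two looks.** The statistics at 50% and 100% information correlate sqrt(0.5) = 0.707. The chance under the null that the interim passes 0.005 or the final passes 0.045 is 0.047. The split does its job for a single test.

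**3. Two phases, either one counting.** The correlation between the two phase changes is not in the documents, so it is an assumption. Both changes use the pre-surgery value. With equal variances and a common correlation r between visits, each change has variance 2(1 - r) and their covariance is r - 1, so they correlate (r - 1)/[2(1 - r)] = -0.5 for any r. Varying r therefore tests nothing, and the phase correlation itself has to be varied. With independent phases the final-analysis error is 1 - (1 - 0.045)² = 0.088. Monte Carlo results from a normal model (8 million draws):

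| Absolute phase correlation | Final only | With 0.005 interim in both phases |
|---|---|---|
| 0 | 0.088 | 0.092 |
| 0.3 | 0.086 | 0.090 |
| 0.5 | 0.082 | 0.085 |
| 0.7 | 0.075 | 0.079 |
| 0.9 | 0.064 | 0.066 |

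A separate simulation of 100,000 null trials using t-tests (17 per arm, 9 per arm at the interim, phase correlation -0.5) gave 8.2% and 8.6%, against 4.7% for a single phase with interim. It used equal spread in both arms and simple changes. It did not model the stated SDs of 1.6 and 0.3 or a per-week rate.

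**4. Other success rules, final analysis, correlation -0.5.**
- Both phases required: 0.045 + 0.045 - 0.082 = 0.008. No inflation.
- Favourable direction only: one phase 0.045/2 = 0.0225; either phase about 2 × 0.0225 = 0.045.

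**5. Interim timing.** Take half of 40 men, no dropout, 1 man per month and 52/12 = 4.33 weeks per month.
- Pre-surgery endpoint: 20 + 4/4.33 = 20.9 to 20 + 16/4.33 = 23.7, so about 21-24 enrolled. The visit one week before surgery makes this about 0.2 of a man earlier.
- 6-month endpoint: add 26/4.33 = 6.0, giving 26.9 to 29.7, so about 27-30 enrolled.
- Counting half of the 34 evaluable men lowers each figure by 3.

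**6. Power once one comparison is named.** At 0.045 with 17 per arm: 0.826 (pooled t) or 0.803 (Welch).

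**The case against.** The best defence is that the pre-surgical phase is plainly meant. The MDSC power calculation is per week and tied to weekly weight loss. Hypothesis 1.1 predicts a fall from baseline, and only the weight loss phase starts at enrollment. The Background reports that the pilot reduction in total MDSCs held steady during maintenance, so no further fall is predicted. This stands as evidence of intent, but it does not settle the matter. The primary objective is worded to include maintenance after surgery, the sample size is inflated for dropout by 6 months, and the only rate the Statistical Analysis section commits to comparing is weight loss.

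A reader might infer that the alpha split itself is faulty. It is not: it gives 4.7% for one test. A reader might also infer that the trial has an 8-9% error rate outright. The documents do not support that, because they state no success rule. The figure applies only if either phase suffices, and the objective's wording, before and after surgery, could be read as requiring both. Nor is 8.2-8.6% the chance of a false claim of benefit. It includes differences favouring control, which could not meet a hypothesis of reduction; the favourable-direction figure is about 4.5%.

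**Conclusion.** The gap is real and should be closed before outcome data are examined. The primary MDSC test has no named phase, and the interim trigger cannot be carried out as written. Conditional on either phase counting, the two-sided error for one marker is about 8.2% (final only) or 8.6% (with interim) at a phase correlation of -0.5. It stays above 5% over the whole assumed range of 0 to 0.9 in absolute value. In the favourable direction it doubles from about 2.2% to 4.5%. If both phases are required there is no excess. The interim would fall at about 21-24 or 27-30 men enrolled, depending on the reading.

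These figures leave aside the choice between total and monocytic MDSC and the within-group paired tests, which are further sources of multiplicity.

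**What to change.** Name one primary comparison: the between-arm difference in change per week, from enrollment to 1 week before surgery, in total MDSC or in whichever single MDSC measure the 17-per-arm calculation used. Saying only MDSC would still leave two tests. Apply 0.005 and 0.045 to that comparison, and trigger the interim when half the men have that value, stating the number.

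Make the maintenance-phase and other MDSC comparisons secondary. Alternatively, test the maintenance phase only after the pre-surgical test succeeds, as a fixed sequence with no division of alpha between phases, using the same thresholds at each look. Align the primary-objective wording in the Synopsis, Aims and Hypothesis, Aim 1 of Research Design and Methods, and Main Outcomes.

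No extra men, visits or assays are needed. The type I error is then about 4.7%, with power of about 0.80-0.83 at 0.045. The price is that a difference seen only after surgery no longer meets the primary objective.

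Keeping both phases primary with a Bonferroni split (0.0025 and 0.0225 per phase) would cut power per phase to 0.70-0.74 and need 20-21 evaluable men per arm for 80%, assuming that the effect and SDs used in the power calculation hold in both phases.
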